### 1.3. Point selection and application of Tongyuan needle method:

Tongyuan acupuncture method was created by [name] in more than 40 years of clinical practice. It has the characteristics of regulating Yin and Yang, regulating yuan and treating God, unique acupoint group, wide indication and remarkable curative effect. Tongyuan needle method is short for the dichotomy of Tongduyangshen and qi qi. According to different diseases or symptoms, the dichotomy can be used in combination or alone, or combined with syndrome differentiation and disease differentiation, or combined with acupuncture and medicine. It breaks through the limitations of the limbs meridian points used in the past, integrates the various forms of acupoint compatibility such as Shu Mu matching, upper and lower matching, left and right matching, and takes the two veins of Ren Du as the focus of meridian point selection, giving full play to the meridians' therapeutic effect of guiding the brain through the channel and regulating the yuan God and Ren pulse connecting the kidney as the return of qi. It is a new acupuncture and moxibustion prescription system of "Fuzhengdispelling evil" and "treating disease must seek the original".

The acupuncture method of Tongyuan includes two parts: Tongdu, qi and yuan. The main points of the head Baihui, the front top, the back top, the seal hall, the middle, the Dazhui, the back of the five viscera are selected; The qi Guiyuan is

mainly composed of Tianshu, Qi Hai, Hui Hui, Guanyuan, Shanzhong, Zhongwan abdominal Ren pulse and Mu points. The two can be used separately and combined, and most of the matching points are five transfusion points below the elbow and knee. Acupuncture and acupoint prescription composed under the guidance of this principle is suitable for many internal injury diseases and difficult diseases, such as female infertility, male infertility and other urogenital diseases, stroke and related encephalopathy, spinal limbs and neuromotor function diseases, dementia, depression, headache, insomnia, intellectual disability, epilepsy and other psychiatric diseases. Chronic cough, bronchial asthma, urticaria, hepatitis, colitis, gastritis, chronic prostatitis, polycystic ovary syndrome and so on have obtained satisfactory curative effect. Some scholars have found that Tongyuan acupuncture can significantly improve the cough reflex ability of patients with tracheotomy after stroke, control lung infection, improve swallowing function, and thus improve the success rate of clinical extubation.

It has been confirmed that scalp acupuncture based on Baihui can improve the volume and area of cerebral infarction [15].

#### 1.4 Research status of acupuncture comfort control design

The design of acupuncture placebo control in clinical trials has always been a difficult point. The ideal acupuncture placebo control should have the following characteristics: first, it has no or very little physiological therapeutic effect; The second is that it is no different or as similar as possible to the trial intervention in every other respect, so that its psychological impact on the patient is minimal, and it is not easy to destroy the blind method. Acupuncture consolation control generally adopts false acupuncture point method or false acupuncture method. The depth of acupuncture can be divided into three degrees: shallow acupuncture, the same depth and non-transdermal. The general requirements of shallow needling are to Pierce the needle body only into the superficial surface of the body about 3~5mm, do not twist and other techniques to avoid qi; The same depth means that the acupuncture body of the comfort acupuncture group and the treatment group have the same depth into the human body; Transdermal is the use of a certain method or needle,

giving people the illusion that the needle body into the human body but does not actually Pierce the skin. The selection of acupuncture sites can be divided into three categories: non-meridian point, different meridian point and the same point. Non-meridian point is no name, no function, no positioning point, including the selection of fixed non-acupoints or false acupoints near the original meridian point (the original acupoint is opened outward by 5~20mm);Different meridian points mean that although they are clear acupoints, they have no therapeutic effect on the disease under study. The same point means that the selected acupoints are consistent with the treatment group [16-17].From the perspective of practical clinical operability and the implementation of the blind method, the control group of this experiment selected the original acupuncture point to open outwards by 1cm, with the same depth of acupuncture.

As for the study on the physiological effects of fake acupuncture points, some scholars collected clinical trial literature that used functional magnetic resonance imaging (fMRI) as the observation index to compare the changes in brain activity after true point acupuncture and fake point acupuncture, and used SDM-PSI software to conduct a meta-analysis of voxel-based whole brain fMRI imaging. It was found that acupuncture at the true point had more significant effects on brain connection, higher nervous function and motor regulation than that at the false point [18].

### 1.5 Current research status of encephalofluctuograph:

Encephalofluctuograph (EFG) is a non-invasive electrophysiological technology used to detect the function of brain neurotransmitters. It collects 10 min brain waves and extracts ultra-slow waves for analysis (frequency range: 1~255 mHz). A large number of experiments have proved that dominant ultra-slow waves are related to the activity of neurotransmitters in brain. Each neurotransmitter has a one-to-one correspondence (cryptographic relationship) with ultra-slow waves of a particular frequency. Through experiments, the code of several common neurotransmitters has been deciphered, which are acetylcholine, norepinephrine, gamma-aminobutyric acid, glutamic acid, 5-hydroxytryptamine and dopamine

[19-20].At present, many domestic scholars have used brain fluctuation graph to study the changes of neurotransmitter power in different nervous system diseases, especially in the study of neurodegenerative diseases, cerebrovascular diseases, emotional disorders and other diseases, and have obtained similar results in different research groups.

He Renhong et al. [21] included 39 patients with brain injury, and then collected the neurotransmitters in the brain during EEG assessment (detected by brain fluctuation map). The detection indexes included the transmitter power, relative power and index analysis of  $\gamma$ -aminobutyric acid, 5-hydroxytryptamine, norepinephrine, dopamine and other transmitters. The results showed that the brain transmitter power of the poor outcome group was significantly lower than that of the good group. Logistic regression analysis showed that gamma-aminobutyric acid and serotonin were the factors that could significantly affect the outcome. The authors suggest that in the clinical rehabilitation of brain injury, therapeutic methods that can improve the efficacy of gamma-aminobutyric acid and serotonin transmitters should be considered.

At present, the study on the effect of acupuncture on awakening has been developed from behavior to molecular mechanism.

## **2.purpose of research**

2.1 Main Objective: To confirm the effect of Tongyuan acupuncture on consciousness disorder after stroke;

2.2 Secondary objective: To explore the mechanism of acupuncture intervention in post-stroke consciousness disorder.

## **3.study endpoint**

3.1 Primary endpoint: GCS score.

3.2 Secondary endpoints: CRS-R Scale (Coma Recovery Scale-Revised), EEG(electroencephalograph), BAEP (Brainstem Auditory Evoked Potential), and EFG (Encephalofluctuography).

## **4.experiment design**

This clinical study was a randomized (1:1), single-blind, single-center, parallel

controlled clinical study. Seventy-two patients were recruited. After signing the informed consent, patients meeting the inclusion/exclusion criteria will be randomly assigned to the experimental group (Tongyuan acupuncture) and the control group (fake acupoint method) in a 1:1 ratio, and a total of 72 patients will be recruited.

Subjects randomized to the trial group will be treated with regular rehabilitation therapy and drug therapy + acupuncture once a day, 5 days a week for 4 weeks. Twenty days in total.

Subjects randomized to the control group will be treated with regular rehabilitation and drug therapy + pseudoacupoint method once a day, 5 days a week for 4 weeks. Twenty days in total.

Safety and study compliance were assessed for each subject at 1, 2, and 3 weeks of initial treatment and at the end of the intervention, and treatment guidance was given by the investigator. A safety assessment and survival follow-up were conducted 4 weeks after discharge, and the corresponding consciousness scale was evaluated.

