| statistic analysis  | 
Analysis set
 
Statistical analysis was carried out using full analysis set, coincidence scheme set and security analysis set.
 
Full analysis set (FAS) : Included all randomised participants who had received at least one study intervention and had a measurable baseline stroke.
 
Per Protocol Set (PPS) : In the FAS population, participants with at least one post-intervention awareness scale assessment, good adherence, and no significant violations or deviations from the trial protocol.
 
Safety Set (SS) : defined as subjects who received at least one intervention and were subsequently evaluated for safety.
 
Sample size determination: The sample size is estimated according to
 |

|                           |  |
|---------------------------|--|
|                           | 
the group design of two sample rates compared sample size estimation formula
 $n = \frac{2 \times (U_\alpha + U_\beta)^2 \times P \times (1-P)}{(P_1 - P_2)^2}$ $P = \frac{(P_1 * n_1 + P_2 * n_2)}{(n_1 + n_2)}$ 
Where, <math>U_\alpha</math> is the first type of error probability <math>U</math> value, <math>U_\beta</math> is the second type of error probability, when bilateral <math>\alpha=0.05</math>, unilateral <math>\beta=0.1</math>, <math>U_\alpha=1.96</math>, <math>U_\beta=1.28</math>, <math>P_1</math> is the effective rate of the treatment group, <math>P_2</math> is the effective rate of the control group, and <math>P</math> is the rate of the two combinations. According to previous research literature [1], <math>P_1</math> and <math>P_2</math> are estimated to be 79.4% and 54.8%, resulting in <math>n \approx 76</math>, and the minimum sample size of each group is about 76 cases. As shedding cases were not excluded during the study, the shedding rate was 15%. For the successful completion of the experiment, 87 cases were assigned to each group based on various factors, and 174 cases were required to be included in the two groups.
 
Statistical analysis: All data in the experiment were tested and analyzed for normality, and SPSS 25.0 statistical software was used for analysis and processing.
 |
| follow-up          | Telephone and video follow-up  |

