| statistical method | Baseline data were analyzed by Chi-square test. Measurement data are expressed as mean SD. Univariate analysis of variance was used to compare the difference between groups at the same time point, the difference at different time points in the group, and the difference before and after between the two groups. $P < 0.05$ was considered statistically significant, and multiple comparisons were performed by Dunnett-t test.   |
| Expected progress  | Clinical cases will be collected from 2023.1.1 to 2024.12.30, and insufficient cases due to shedding will be added from 2025.1.1 to 2025.12.30.  |

List of abbreviations and term definitions

| abbreviation | definition                          |
|---------------------|--|
| CRS-R               | Coma Recovery Scale-Revised                |
| GCS                 | glasgow coma scale                         |
| NIHSS               | National Institutes of Health Stroke Scale |
| FOUR                | Full Outline of Unresponsiveness Scale     |

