## **13. statistic analysis**

### **13.1 Sample size determination**

In this study, 1:1 parallel control was used to estimate the sample size according to the group design of two sample rates comparison sample content estimation formula:

$$n = \frac{2 \times (U_\alpha + U_\beta)^2 \times P \times (1-P)}{(P_1 - P_2)^2} \quad P = \frac{(P_1 * n_1 + P_2 * n_2)}{(n_1 + n_2)}$$

Where,  $U_\alpha$  is the first type of error probability  $U$  value,  $U_\beta$  is the second type of error probability, when bilateral  $\alpha=0.05$ , unilateral  $\beta=0.1$ ,  $U_\alpha=1.96$ ,  $U_\beta=1.28$ ,  $P_1$  is the effective rate of the treatment group,  $P_2$  is the effective rate of the control group, and  $P$  is the rate of the two combinations. According to previous research literature,  $P_1$  and  $P_2$  are estimated to be 79.4% and 54.8%, resulting in  $n \approx 76$ , and the minimum sample size of each group is about 76 cases. As shedding cases were not excluded during the study, the shedding rate was 15%. For the successful completion of the experiment, 87 cases were assigned to each group based on various factors, and 174 cases were required to be included in the two groups.

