#### **14.4 The expected schedule and completion date of the clinical trial**

- 1)2023.1.1~2024.12.30: Clinical cases were collected
- 2)2025.1.1~2025.12.30: Cases of deficiency due to supplementary Shedding

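### Section 4 sets total recruitment at 72, while the Summary and Section 13.1 require 174; at 72 the comparison used for sizing has about 60% power, not 90%

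*Combined protocol and SAP*

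**What the plan says.** Section 4 (experiment design) describes a single-centre trial randomised 1:1 and states its size twice in one paragraph, once in words and once in digits: "Seventy-two patients were recruited" and "a total of 72 patients will be recruited". At 1:1 that is 36 per group.

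The Summary of research scheme lists a sample size of 174 and gives the calculation behind it, ending with "174 cases were required to be included in the two groups". Section 13.1 repeats the calculation. It concludes that "the minimum sample size of each group is about 76 cases", cites a 15% shedding rate, and then states that "87 cases were assigned to each group based on various factors, and 174 cases were required to be included in the two groups".

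Two passages bear on how the total is counted. The expected-progress row of the Summary says that "insufficient cases due to shedding will be added from 2025.1.1 to 2025.12.30". Section 14.4 gives the same period to "Cases of deficiency due to supplementary Shedding". Neither gives a number.

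The sample size is calculated for a difference in effective rates. Section 3 names the endpoint as "Primary endpoint: GCS score", and Section 13.3 plans analysis of variance on scale scores.

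**The concern.** Total enrolment is a basic design parameter, and the protocol gives two values that differ by a factor of 2.4 (174/72). The second statement in Section 4 is explicitly a total, so 72 cannot be read as a per-group figure. No pilot, interim stage or subset is described that would account for it.

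Section 4 is where an ethics committee or the study team would look for the number to recruit. If it is followed, enrolment stops at 41% of the derived number (72/174), and the trial has a poor chance of showing the effective-rate difference it was sized for. If 72 is only leftover text, the design section still misstates the trial's size, and a final enrolment near either number could be presented as the planned one.

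**Working it through.** **Inputs** (Section 13.1, repeated in the Summary): P1 = 0.794, P2 = 0.548, two-sided alpha 0.05 (U = 1.96), beta 0.1 (U = 1.28), 1:1 allocation, shedding 15%.

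**Reproducing the plan's figure.** With equal groups, P = (0.794 + 0.548)/2 = 0.671 and P1 − P2 = 0.246.

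n = 2 × (1.96 + 1.28)² × 0.671 × 0.329 / 0.246² = 76.6 per group.

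This agrees with the stated value of about 76. Then 76 × 1.15 = 87.4, which matches 87 per group and 174 in total. That the 15% was applied this way is an inference, since the text attributes 87 only to various factors.

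**Can the same inputs give 36 per group?** No standard variant does. The two-proportion formula with pooled variance under the null and separate variances under the alternative (Fleiss) gives 75 per group, 83 with continuity correction, and 61 if the test is made one-sided at 0.05.

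**Power at each size.** Turning the plan's formula round gives

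power = Φ( √[ n × 0.246² / (2 × 0.671 × 0.329) ] − 1.96 ).

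For n = 36: √(36 × 0.060516 / 0.441518) = 2.221; 2.221 − 1.96 = 0.261; Φ(0.261) = 0.603.

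| Evaluable per group | Where it comes from | Plan's formula | Fleiss | Exact, uncorrected chi-square |
|---|---|---|---|---|
| 36 | 72 in total, no loss | 60.3% | 60.7% | 62.6% |
| 31 | 36 × 0.85 = 30.6 | 54.0% | 54.2% | 54.8% |
| 74 | 87 × 0.85 = 73.95 | 89.0% | 89.8% | 90.0% |
| 76 | stated minimum | 89.8% | 90.5% | 90.6% |
| 87 | 174 in total, no loss | 93.2% | 93.9% | 94.0% |

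With Fisher's exact test or a continuity-corrected test, exact power at 36 per group falls to about 52%.

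**What 36 per group could detect.** Holding P2 at 0.548 and solving the plan's formula for n = 36 gives P1 = 0.891. Check: P = 0.7195, and 2 × 10.4976 × 0.7195 × 0.2805 / 0.343² = 36.0. So 90% power would need a difference of about 34 percentage points, against the 24.6 assumed.

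**Secondary: the loss allowance.** A 15% loss from 87 is about 13 patients and leaves about 74 per group, roughly 2 below the stated minimum. The 87 covers a loss of up to 1 − 76/87 = 12.6% (11.5% if 76.6 is rounded up to 77). The table shows that this matters little: power at 74 is within about one point of 90%.

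**The case against.** The strongest reply is that 72 is a leftover and the trial is not underpowered. 174 appears in the Summary's sample-size row and in two full derivations, while 72 appears in one paragraph with no derivation. The protocol carries other text that does not fit this trial: a history of HCC in Section 7.1, an investigational drug in Section 13.2, genetic data in Section 14.2, and a multi-centre report in Section 14.5.2 although Section 4 describes a single centre. That makes leftover text plausible, but nothing in the documents confirms it. The loss of power is therefore conditional on 72 being followed; the conflict between the two totals is not.

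A second reply is that 60% is not the power of the planned analysis. This is correct. Chi-square is named only for baseline data, no test of the effective rate is specified for efficacy, and the primary endpoint is to be analysed as a score. Section 8.1.1 does define effectiveness from the percentage change in GCS, so the sizing quantity is tied to the primary scale, but the 60% describes the sizing comparison only.

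A third reply is that the loss allowance is a matter of convention with negligible effect, and that replacement is already planned. The effect is indeed small. What remains is that the documents do not say whether 174 includes the replacements.

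**Conclusion.** The concern holds. The current text gives two totals, 72 and 174, and does not reconcile them; only 174 has a derivation, and that derivation reproduces. It must be fixed because the recruitment target is contradictory, whichever number is in use.

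If 72 is followed, power for the sizing comparison is about 60% with every patient evaluable (60% to 63% by formula or exact uncorrected chi-square) and about 54% to 55% after 15% loss, against the stated 90%. These figures assume 79.4% versus 54.8%, two-sided 0.05 and equal groups. They do not carry over to the analysis of variance of GCS scores: the documents give no standard deviation, so its power cannot be computed at 72 or at 174.

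The loss allowance is minor and would not by itself call for a change in sample size.

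**What to change.** In Section 4, replace both statements of 72 with the Section 13.1 figure, 174 in total and 87 per group, with the sponsor confirming that this is the target in use.

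In Section 13.1, without enrolling more patients, add:

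- one sentence saying that, for the effective-rate comparison, 15% loss before any replacement leaves about 74 per group with power of about 89% to 90% (equivalently, that 174 covers about 12.6% loss at 76 evaluable per group);
- one sentence saying whether 174 is counted before or after the 2025 replacement of shed cases, so that the section agrees with the Summary's expected progress and Section 14.4.

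If 174 is the target in use, as the Summary and the only derivation indicate, the cost is a wording change in two sections. If recruitment is in fact running to 72, the correction changes enrolment and not only text; the documents do not settle which.

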## Summary of research scheme

|                            |  |
|----------------------------|--|
| scheme name         | Study on the effect of Tongyuan acupuncture on consciousness disorder after stroke   |
| applicant           | Nanfang Hospital, Southern Medical University  |
| major investigators |  |
| research center     | Department of Rehabilitation, Nanfang Hospital, Southern Medical University  |
| research object     | Stroke patients with conscious disturbance   |
| purpose of research | Objective: To investigate whether Tongyuan acupuncture can improve the consciousness disorder after stroke
Secondary objective: To investigate the possible mechanism of action   |
| Research grouping   | Trial group: Tong Yuan acupuncture, once a day, 5 days a week for 4 consecutive weeks.Twenty days in total.
Control group: pseudoacupoint method, once a day, 5 days a week for 4 consecutive weeks.Twenty days in total.   |
| study design        | This study was a randomized, placebo-controlled, single-blind study. Patients with post-stroke consciousness disorder hospitalized in the rehabilitation Department of Southern Hospital were randomly included into the experimental group and the control group, and the experimental group was treated with Tongyuan acupuncture on the basis of routine rehabilitation treatment and drug treatment. The control group was treated with 1cm acupuncture at the same depth beside the selected points of the experimental group. Before intervention, treatment for 1 week, treatment for 2 weeks, treatment for 3 weeks, and treatment for 4 weeks (after completion), follow-up:GCS score, CRS-R scale (Modified Coma Recovery Scale) were performed 4 weeks after discharge to assess the conscious state of the patients, and EEG, brainstem evoked potential and brain fluctuation map were examined before intervention and 4 weeks after treatment. The baseline data of the experimental group and the control group showed no statistical difference through statistical analysis. Conventional rehabilitation treatment and drug treatment were adopted by the current guidelines, and the distribution of cases in the two groups was also random. |
| Study duration      | 2023.1.1-2025.12.31  |
| sample size         | 174  |

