### Test flow chart

| item                                 | Screening period |                  | Duration of treatment (weeks) |   |   |   | Four weeks after discharge | Quit |
|--------------------------------------|------------------|------------------|-------------------------------|---|---|---|----------------------------|------|
|                                      | 4week s~2days    | base line /-1day | 1                             | 2 | 3 | 4 | Phone or video follow-up   |      |
| Informed consent                     | X                |                  |                               |   |   |   |                            |      |
| Demography                           | X                |                  |                               |   |   |   |                            |      |
| Inclusion/exclusion criteria         | X                |                  |                               |   |   |   |                            |      |
| Medical history                      | X                |                  |                               |   |   |   |                            |      |
| CRS-R scale                          |                  | X                | X                             | X | X | X | X                          |      |
| GCS score                            |                  | X                | X                             | X | X | X | X                          |      |
| NIHSS score                          |                  | X                | X                             | X | X | X | X                          |      |
| FOUR score                           |                  | X                | X                             | X | X | X | X                          |      |
| Electroencephalogram                 |                  | X                |                               |   |   | X |                            |      |
| brainstem auditory evoked potentials |                  | X                |                               |   |   |   | X                          |      |
| encephalofluctuograph                |                  | X                |                               |   |   |   | X                          |      |

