Ma Liang et al. [12] took 60 patients with consciousness disorder after craniocerebral injury as research objects. The control group was treated with routine awakening promotion method, and the observation group was treated with Tongdu Xingnao acupuncture method on the basis of the control group. It was found that the total effective rate of the observation group was significantly higher than that of the control group ( $P < 0.05$ ). The waking time, feeding time, getting out of bed time and discharge time of observation group were shorter than those of control group ( $P < 0.05$ ). After treatment, the scores of the revised Coma Recovery Scale (CRS-R) and Total non-responsiveness Scale (FOUR) in the observation group were higher than those in the control group ( $P < 0.05$ ). After treatment, the levels of neuron-specific enolase (NSE) and astroglia-derived protein (S100 $\beta$ ) in observation group were lower than those in control group, and the levels of brain-derived neurotrophic factor (BDNF) and nerve growth factor (NGF) in observation group were higher than those in control group ( $P < 0.05$ ).

Ma Qian et al. [13] included 91 cases of acute stroke patients with

consciousness disorder for study, and the acupuncture group was given the treatment of wakefulness and resuscitation acupuncture. There was significant difference in Glasgow scores between the acupuncture group and the control group at 10 and 20 days of treatment.

Xu Junfeng et al. [14] applied head electroacupuncture across the Central Line, used high-intensity stimulation combined with amplitude modulation, frequency conversion, instantaneous stimulation and continuous stimulation, and combined with integrated rehabilitation programs of traditional Chinese and Western medicine, Western medicine, exercise therapy, sensory stimulation and other traditional Chinese and western medicine, and achieved certain effects on the awakening of patients with persistent vegetative state.

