## **7. Research methods and procedures**

All subjects need to sign informed consent before screening, and successful subjects can enter this study. According to the protocol, the experimental group and the control group were treated respectively, and the effectiveness and safety were evaluated at 1, 2, 3 and 4 weeks. Telephone and video follow-up were conducted 4 weeks after discharge for statistical analysis. Treatment continued until subjects completed the 4-week course or met any of the exit criteria. Participants are evaluated comprehensively by the investigator, and if it is determined that the continuation of the experimental treatment can bring clinical benefit to the subject, the treatment can be continued until the subject's PD, intolerance, or death.

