### **(2) Evaluation:**

Consciousness levels were assessed before intervention, at 1, 2, 3, and 4 weeks of treatment, and 4 weeks after discharge: GCS score, NIHSS score, CRS-R Scale (Modified Coma Recovery Scale), and FOUR scale score . Electroencephalogram, brainstem auditory evoked potentials and encephalofluctuograph were examined before intervention and at 4 weeks of treatment.

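### Follow-up consciousness scores are timed from discharge, which treatment may influence, so the follow-up comparison can mix treatment effect with a difference in elapsed time

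*Combined protocol and SAP*

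**What the plan says.** Each place that times the last consciousness assessment ties it to discharge.

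- **Summary, study design:** GCS and CRS-R "were performed 4 weeks after discharge to assess the conscious state of the patients".
- **Test flow chart:** the last assessment column is headed "Four weeks after discharge", with CRS-R, GCS, NIHSS and FOUR all marked in it.
- **Section 4:** "A safety assessment and survival follow-up were conducted 4 weeks after discharge, and the corresponding consciousness scale was evaluated".
- **Section 7:** "Telephone and video follow-up were conducted 4 weeks after discharge for statistical analysis".
- **Section 7.2(2):** "Consciousness levels were assessed before intervention, at 1, 2, 3, and 4 weeks of treatment, and 4 weeks after discharge".

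Section 7.3 lists the four scales for the follow-up period and gives no timing. No section states a fixed week for this visit, a visit window, a discharge criterion or a planned length of stay.

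Section 13.3 compares the groups by univariate analysis of variance at each common time point, with no term for elapsed time. Section 8.1 names the week-4 GCS for the effectiveness evaluation. Section 3.1 names GCS as the primary endpoint without a time point.

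**The concern.** Baseline and weeks 1 to 4 are tied to the start of treatment, so both groups are scored at the same elapsed time. The last visit is tied to an event after randomisation, and the protocol itself gives two reasons to think treatment could move that event.

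- Section 1.2 cites an acupuncture trial in consciousness disorder in which the "discharge time of observation group were shorter than those of control group". That trial was in craniocerebral injury, not stroke.
- Section 7 lets treatment run beyond four weeks "if it is determined that the continuation of the experimental treatment can bring clinical benefit to the subject", so time in hospital may depend on how the patient responds.

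If stay differs between groups, what the analysis treats as one time point is two different mean times on the recovery curve. The follow-up contrast then no longer estimates the treatment difference at a defined time. Section 7 sends these data to the statistical analysis, and Section 3.1 does not exclude the follow-up GCS from the primary endpoint.

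**Working it through.** The plan gives no figure on this point, so there is none to reproduce. The structure follows from the schedule.

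**Step 1: when the visit falls.** Let S be the weeks from randomisation to discharge, taking treatment to start at randomisation. The follow-up is at

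T = S + 4 weeks.

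If S ran from 4 to 12 weeks (assumption), T would run from 8 to 16 weeks. The week 1 to 4 visits have no S in them.

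**Step 2: difference between groups.** Let d be mean S in the acupuncture group minus mean S in the control group. The 4 weeks cancel, so mean T also differs by d.

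**Step 3: effect on the score contrast.** Suppose GCS is rising by b points per week in both groups around the visit (assumption). Then

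follow-up contrast = difference at a common time + b × d.

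| d (weeks, assumed) | b (points/week, assumed) | Shift b × d |
|---|---|---|
| −1 (acupuncture leaves earlier) | 0.2 to 0.5 | −0.2 to −0.5, against acupuncture |
| 0 | any | 0 |
| +1 (acupuncture leaves later) | 0.2 to 0.5 | +0.2 to +0.5, in favour of acupuncture |

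**Step 4: scale.** With an assumed GCS standard deviation of 3 and the 76 per group of Section 13.1, the standard error of the difference is 3 × √(2/76) = 0.49. A shift of 0.2 to 0.5 is then about 0.4 to 1.0 standard errors (0.2/0.49 and 0.5/0.49).

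**Step 5: what the documents fix.** They give none of S, d, b or the GCS standard deviation. The sign of d is open: the cited trial points to earlier discharge with acupuncture, while the extension clause in Section 7 could keep responders in hospital longer. Only the structure in Steps 1 and 2 comes from the protocol.

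**The case against.** **The main efficacy result is not touched.** Section 8.1 evaluates GCS at week 4 of treatment, and all on-treatment visits are timed from treatment. This stands. A reader might infer that the trial's principal comparison is biased, but the documents support that only if the follow-up GCS is used for the primary claim, which Section 3.1 leaves open.

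**Randomisation and blinding protect the comparison.** If treatment changes neither recovery, complications nor stay, randomised groups with patients, families and evaluators blinded as Section 4.2.2 describes have the same expected discharge time, so the expected shift is zero. This also stands. It would be wrong to present the 0.2 to 0.5 points as an artefact of a wholly inert treatment. Blinding does not help, however, once treatment itself alters stay.

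**An effective treatment would be penalised.** A reader might infer this from the cited trial. That trial was in another condition and compared acupuncture plus routine care with routine care, not with sham needling. Extended treatment could push the other way, so the direction is not settled.

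**Inpatients drop out of the visit.** A reader might infer this too. Those with long stays reach it late rather than never, and Section 11 keeps the trial open for at least six months of survival follow-up. In-hospital deaths do miss it, but they would miss a fixed-date visit as well.

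**A fixed date has its own drawback.** Follow-up is planned by telephone or video. A fixed date means that some patients are still in hospital, so assessment mode could track discharge. This is a real cost, though it can be reduced.

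**Conclusion.** The point holds for the follow-up comparison of GCS, CRS-R, NIHSS and FOUR. As timed, that comparison can mix treatment effect with a difference in time since randomisation whenever treatment changes length of stay, and nothing in the schedule or analysis prevents or adjusts for this. Confidence is high on the wording of the anchor. There is no documentary basis for a direction or a size: the 0.2 to 0.5 points rest on an assumed 1-week difference in mean stay and an assumed slope of 0.2 to 0.5 points per week.

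This is a secondary design weakness that should be corrected, not a defect in the week-4 result. Its weight depends on whether follow-up scores will support an efficacy claim.

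**What to change.** For the consciousness scales only, replace the discharge anchor in the Summary, the flow chart and Sections 4, 7 and 7.2(2) with a fixed time from randomisation for every patient, discharged or not, and state the same time in Section 7.3. Eight weeks (4 weeks after the planned end of treatment) with a window of 1 week either side is one reasonable choice. Record the discharge date, the mode of assessment and vital status at that time, so that both groups' deaths are counted to the same point.

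Leave the post-discharge safety and survival contact in Section 4 and the adverse-event follow-up in Section 8.2 as they are.

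The cost is protocol wording and scheduling, with no change in sample size. Where the fixed date does not coincide with the post-discharge safety contact, a separate contact is needed. Some assessments will be at the bedside and some remote. Use the same remote or video procedure for all patients where feasible, and report results by mode.
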